
¹ Screening and Baseline may occur on the same day. If this occurs, lesion count and review of inclusion/exclusion criteria will only occur once.
 
² All visit dates are in reference to Baseline (e.g. Week 2 occurs 14 days after Baseline Visit). The Week 4 visit may be performed remotely or in clinic. Baseline, Week 2, Week 8, Week 12, and 24 visits will be performed in clinic. Day 2, Week 16, and Week 20 will be performed via phone. If a subject terminates early, an in-clinic visit is preferred, but a remote visit may be performed with sponsor approval.
 
³ Lesion counts will be performed twice during the Baseline visit; the first assessment will be performed by the investigator in person, and the second assessment will be performed by the investigator through image evaluation.
 
⁵ The physical exam will include a directed examination of the skin (presence or absence of individual features of erythema, flaking/scaling, crusting, swelling, vesiculation/pustulation, and erosion/ulceration).
 
⁶ Females who have reached 9 years of age, unless they are post-menopausal (at least 12 months of continuous amenorrhea without an alternative medical cause), or surgically sterilized (documented hysterectomy, documented bilateral salpingectomy, or documented bilateral oophorectomy). Tubal ligation does not meet the definition of surgically sterile.
 
⁷ UPT will be performed at Screening if the visit takes place in the clinic.
 
⁸ BOTE Inflammation Score will be assessed pre-dose at Baseline. The Baseline LSR assessment should be done at least 30 minutes after study drug is applied on Day 1. After Baseline, BOTE Inflammation score and LSRs can be evaluated at any time pre- or post-dose during the visit, regardless of whether lesions are present and whether study drug is applied.
 
⁹ Study drug application will occur in clinic at Baseline, Week 2, Week 4, Week 8, and Week 12. On days when a remote visit will occur, subjects/caregivers will not apply the study drug until the study visit so that the mixing/application of study drug can be observed by site staff during the remote visit.
 
¹⁰ At Screening, subjects should be asked if any household members currently have MC. In addition to recording AE and CM changes, subjects should be asked if there are any new occurrences of MC in household members of subjects at each visit, except Day 2.
 
¹¹ Follow up interviews will be performed with selected consented subjects that complete Week 12. Consent can be obtained starting at Baseline, and the follow up interview will be performed with the subject/caregiver at a later date.
 
NOTE: The Week 4 visit can be performed in clinic or remote. Baseline, Week 2, Week 8, Week 12, and Week 24 should be performed in clinic wherever possible. Day 2, Week 16, Week 20 should be performed as telephone contacts. Unscheduled visits are permitted as needed for medical reasons. In-clinic unscheduled visits should be reserved for evaluation of adverse events, lesion clearance, and study drug dispensation as needed. Remote unscheduled visits may be utilized as well as/if applicable.
			

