6.6 Order of Assessments

At the Baseline visit on Day 1, the physical examination and BOTE Inflammation Score should be done prior to randomization to study treatment. For WOCBP (see definition in Section 9.4), the UPT must be done prior to randomization. The initial Local Skin Reaction (LSR) assessment should be done at least 30 minutes after study drug is applied on Day 1. The BOTE and LSR assessments should be completed at each scheduled visit even if the subject is not going to be dosed or if the MC lesions have cleared. It may be most convenient to perform lesion counting, mapping, and scarring assessments immediately following the BOTE and LSR assessments. In order to ensure consistent counting of MC lesions, the same assessor should complete the lesion counts at all visits, but at a minimum, at Baseline and Week 12.

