7.1.2 Other Assessments

7.1.2.1 BOTE Inflammation Score

Inflammatory reactions around MC lesions has been associated with imminent resolution of MC (sometimes referred to as “beginning-of-the-end” [“BOTE”] signs). Investigators should educate subjects and caregivers on the characteristic stages of BOTE as it is recognized as the natural course of self-limiting clearance of MC. BOTE may be associated with itching, but not pain. BOTE is usually asymptomatic, self-limited, localized to individual MC lesions, and does not require discontinuation of study treatment or additional treatment.

Investigators will assess the treatment area at each scheduled visit and use their medical judgement to differentiate between BOTE and LSRs. The BOTE Inflammation Score will be recorded at each visit ([Table 5](#)).

Table 5 BOTE Inflammation Score

Score	Global Assessment	Description
0	No inflammation	No evidence of local inflammation
1	Mild	Minimal erythema and/or edema
2	Moderate	Definite erythema and/or edema with or without hemorrhagic crusting
3	Severe	Erythema and edema with definite hemorrhagic crusting
4	Very Severe	Strong reaction spreading beyond the treated area, bullous reaction, erosions

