Subjects who discontinue the study prior to the Week 12 visit will be asked to complete the Week 12 visit assessments in the clinic: this will be recorded as an Early Termination (ET1) visit. Subjects who discontinue from the study after Week 12 but prior to Week 24 will be asked to come to the site to complete Week 24 assessments; this will be recorded as an ET2 visit.

Safety assessments include BOTE Inflammation Scores, local skin reaction (LSR) scores, AE collection, including scarring/keloid, and urine pregnancy tests. Safety assessments will be completed at specified visits through Week 12. Adverse events and concomitant medications will be reviewed and updated as needed at each visit through Week 24.

Inflammatory reactions around the MC lesions has been associated with imminent resolution of MC (sometimes referred to as "beginning-of-the-end" ["BOTE"] sign). The investigator (or designated evaluator) will assess the presence and overall degree of inflammatory reactions at MC lesions at Baseline (pre-dose) and Weeks 2 through 12 using the BOTE Inflammation Score in the table below. BOTE may be associated with itch, but not pain. BOTE is usually asymptomatic, self-limited, and localized to individual MC lesions and does not require discontinuation of study treatment or additional treatment. LSR is generally more diffuse, associated with significant itch or tenderness, may necessitate discontinuation of study treatment, and may need treatment for symptomatic relief (e.g., a topical corticosteroid or topical anesthetic). For very severe LSR, systemic corticosteroids may be considered. Investigators will assess the treatment area at each scheduled visit and use their medical judgement to differentiate between BOTE and LSR. BOTE Inflammation Score and LSR component scores will be recorded at each visit. BOTE should not be considered an AE. When LSRs are clinically significant at the application site, the investigator should report the condition as an AE(s).

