The process for SAS program validation and quality control (QC) for programs and outputs is documented in the Synteract working instruction “SAS programming quality control.” Study-specific QC requirements can be found in Appendix B: SAS Programming QC Requirements.

The study treatment period is defined from randomization through completion of Week 12/ET1 visit and the safety follow-up period is from the completion of Week 12 through the completion of Week 24/ET2 visit.

After all subjects have completed their Week 12/ET1 visit, thus completing the Treatment Period of the study, the database through Week 12/ET1 will be frozen and unblinded for purposes of the primary analysis of efficacy and safety. While this analysis is being prepared, the subjects will continue through Week 24/ET2. After all subjects have completed their Week 24/ET2 visit, the database will be locked and the follow-up data will be analyzed.

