## 12. OTHER ANALYSES

The following analyses of BOTE vs lesion count will be presented:

- Percent change from Baseline in the number of treatable MC at each visit in relation to the Baseline BOTE score comparing No Inflammation vs Inflammation within each treatment group through a repeated measures mixed model with number of randomly assigned subjects in household (1 subject vs 2 subjects), investigator type (dermatologist

vs other), BOTE score at Baseline (no inflammation [BOTE=0] vs mild/moderate/severe/very severe inflammation [BOTE $\geq$ 1]), BOTE score at Baseline by visit interaction, age, and baseline lesion count as covariates with a compound symmetry covariance matrix.

- Percent change from Baseline in the number of treatable MC at Week 12 in relation to the highest post-baseline BOTE score during treatment will be summarized descriptively.
- Percent change from Baseline in the number of treatable MC at Week 12 in relation to the highest BOTE score at any visit (including Baseline) will be summarized descriptively.
- Percent change from Baseline in the number of treatable MC at each visit in relation to the BOTE score at Week 2 will be summarized descriptively.

In these analyses, the BOTE scores will be analyzed in the ITT Population as follows:

1. Dichotomized:
  - a. Score of 0: No Inflammation
  - b. Score of 1, 2, 3, or 4: Mild to Very Severe

A shift table comparing the baseline BOTE score to each scheduled post-baseline assessment will be presented for the ITT Population.

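### SAP 12 relates Week 12 lesion change to the highest BOTE score in a window that includes Week 12, which can bias two descriptive tables against the inflamed group and hide a real link with resolution

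*SAP*

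**What the plan says.** SAP 12 lists four analyses of BOTE against lesion count. The second summarizes percent change at Week 12 "in relation to the highest post-baseline BOTE score during treatment will be summarized descriptively". The third uses the same outcome "in relation to the highest BOTE score at any visit (including Baseline) will be summarized descriptively". Both use a dichotomy in which the upper group is "Score of 1, 2, 3, or 4: Mild to Very Severe", so one score of 1 at any visit puts a subject in the inflamed group. Appendix C lists them as Tables 14.2.3.12.2 and 14.2.3.12.3.

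On timing, SAP 6 states: "The study treatment period is defined from randomization through completion of Week 12/ET1 visit". SAP 4 has the investigator grade "inflammatory reactions at MC lesions at Baseline (pre-dose) and Weeks 2 through 12 using the BOTE Inflammation Score". Neither table has a lag, a landmark or a restriction to subjects who still have lesions.

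On scoring after clearance, Protocol 6.6 requires the BOTE and LSR assessments to be "completed at each scheduled visit even if the subject is not going to be dosed or if the MC lesions have cleared". A footnote to the Schedule of Assessments (Protocol 1.2) says that after Baseline they can be done "regardless of whether lesions are present and whether study drug is applied".

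The other two analyses in SAP 12 fix the BOTE score early: a mixed model on Baseline BOTE and a summary by Week 2 BOTE.

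**The concern.** The clinical idea behind these tables is given in Protocol 7.1.2.1: "Inflammatory reactions around MC lesions has been associated with imminent resolution of MC". A useful table would show whether inflammation seen at one time is followed by resolution later.

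The highest-score tables do not keep that order. Inflammation first seen at Week 12 cannot have led to the Week 12 count. In addition, a subject who clears at Week 4 or 8 and stays clear has fewer visits with a lesion to be inflamed than a subject who never clears. If cleared skin mostly scores 0, the grouping depends partly on the outcome that it is meant to explain, and the inflamed group collects subjects who did not clear. A reader could then underrate BOTE as a sign of resolution. Protocol 3 lists evaluation of BOTE as an objective, and BOTE is a stratification factor.

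**Working it through.** The plan states no figure for these tables, so there is none to reproduce. The checks ask how large the artefact could be and what it depends on.

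**1. Closed form, no true link.** Document inputs (Protocol 2.1.4.3, NI-MC302, SB206): complete clearance 13.9% at Week 8 and 30.0% at Week 12. Assumptions: probability p = 0.2 of BOTE ≥1 at a visit with lesions, independent between visits, 0 once clear, no recurrence. Subjects clear at Week 8 had 2 lesion-bearing visits (Weeks 2 and 4), those first clear at Week 12 had 3, and the rest had 4.

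P(ever inflamed) = 1 − (1 − p)^k gives 36.0% for k = 2, 48.8% for k = 3 and 59.0% for k = 4.

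- Inflamed and clear: 0.139 × 0.360 + 0.161 × 0.488 = 0.1286
- Inflamed and not clear: 0.700 × 0.5904 = 0.4133
- Clearance if inflamed: 0.1286 / 0.5419 = 23.7%
- Clearance if not inflamed: 0.1714 / (0.1714 + 0.2867) = 37.4%

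In the mildest case, where every clearer misses only the Week 12 visit, the figures are 26.2% vs 34.9%. The inflamed group looks worse for every p from 0.1 to 0.4 in both arms of both earlier phase 3 studies.

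**2. Dropping only the Week 12 score.** Subjects who never clear then have k = 3, so inflamed and not clear is 0.700 × 0.488 = 0.3416. Clearance is 0.1286 / 0.4702 = 27.4% vs 0.1714 / (0.1714 + 0.3584) = 32.4%. Some bias remains.

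**3. Simulation, varying the assumptions.** 1,000,000 subjects; clearance 2/5/14.5/28% by Weeks 2/4/8/12 (Weeks 8 and 12 are close to the earlier SB206 rates, Weeks 2 and 4 are assumed); BOTE ≥1 at 30% per lesion-bearing visit. The true link is an odds ratio (OR) for clearance by the next visit. Entries are percent clear at Week 12, ever vs never inflamed. Repeat runs agree within about 0.2 points.

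| Assumption | No link | OR 3 |
|---|---|---|
| Independent visits, cleared skin scores 0 | 21.1 vs 43.6 | 25.4 vs 34.1 |
| Independent visits, cleared skin scores ≥1 half as often | 25.1 vs 35.7 | 28.5 vs 26.7 |
| Correlation 0.5 on a latent normal scale, cleared skin scores 0 | 22.4 vs 34.7 | 29.5 vs 26.2 |
| Correlation 0.5 from a subject-level beta probability, cleared skin scores 0 | 23 vs 32 | 32.2 vs 24.2 |

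With no link the inflamed group looks worse in every row. An OR of 3 is reversed only in the first row. An OR of 2 in the second setting is still reversed (27.1 vs 30.3).

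**4. The outcome that the SAP uses.** The tables report percent change, not clearance. A lesion-count simulation (200,000 subjects, about 25% clear at Week 12, p = 0.2, independent visits, cleared skin scoring 0) gives these means:

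| True effect of BOTE on the next interval's resolution rate | Inflamed | Not inflamed |
|---|---|---|
| None | −45.4 | −56.7 |
| Doubled | −48.4 | −53.0 |
| Tripled | −50.0 | −50.6 |

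Over p = 0.1 to 0.3 the doubled link is reversed each time. The tripled link ranges from slightly correct (−51.3 vs −49.9) to reversed (−49.4 vs −51.5). If cleared skin scores ≥1 as often as lesional skin, the no-link artefact vanishes (−50.8 vs −50.5). With no link, the planned Week 2 summary gives −50.3 vs −50.8, which is nearly unbiased.

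**The case against.** The strongest reply is that the protocol requires BOTE scoring after clearance, so all subjects attending have the same number of scored visits. That is correct. The imbalance is in lesion-bearing visits, and it matters only if cleared skin scores lower. No section says that it scores 0. Some text points the other way: Protocol Table 5 grades local inflammation up to a reaction spreading beyond the treated area, Protocol 4.1 has subjects keep treating an area until the next visit even if lesions clear, and Protocol 2.1.4.2 reports application-site erythema on SB206. Against this, SAP 4 and Protocol 4.1 describe BOTE as inflammation at MC lesions and ask investigators to tell it apart from local skin reactions, so lower scoring of cleared skin is plausible but not established.

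A reader might infer that the tables will show the link backwards. The documents do not support that. Reversal needs a particular combination: independent visits, cleared skin scoring at or near 0, and a weak to moderate link. With persistent within-subject inflammation, an OR of 3 shows in the right direction.

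The Baseline and Week 2 analyses stand beside these tables, are time-ordered and are largely free of the problem. The SAP does not call the highest-score tables predictive. Both facts reduce the stakes. What remains is that neither analysis covers inflammation arising at Weeks 4 or 8, and the tables meant to cover it have the outcome inside the grouping window.

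**Conclusion.** The point holds as a possible bias of unknown size. If cleared skin is scored ≥1 less often than skin with lesions, both tables are biased toward worse outcomes in the inflamed group. They can then hide a true link, or reverse it under some assumptions. With no true link, the spurious gap in Week 12 clearance in the settings shown runs from about 9 points (26.2% vs 34.9%; 23% vs 32%) to about 22 points (21.1% vs 43.6%). These figures rest on assumed BOTE frequencies, which the documents do not give, and on no recurrence after clearance. There is no bias if cleared skin scores as often as lesional skin.

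Severity is minor. The tables are descriptive, lie outside the fixed testing sequence, and cannot affect the primary result, alpha or power.

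**What to change.** Add, or substitute for the two tables, a time-ordered summary by arm. Among subjects with at least one treatable lesion at Week 2, 4 or 8, show lesion-count change and clearance at the next scheduled visit by BOTE (0 vs ≥1) at the current visit. Report each interval separately, because they last 2, 4 and 4 weeks. In the simulation at 30% BOTE per visit, pooled over intervals, this comparison gives 9.3% vs 9.3% clearance with no link and 16.3% vs 6.4% with an OR of 3.

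If the highest-score tables are kept, use only scores before Week 12 and footnote that they are not predictive. The footnote is needed because removing Week 12 alone leaves residual bias.

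Cost: SAP wording and two table shells, using data already collected. If the tables are replaced, the simple ever-inflamed description at Week 12 is lost.

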### 13. SAFETY ANALYSES

All safety analyses will be based on the Safety Population.

A listing of all deaths will be presented.

#### 13.1 Adverse Events

Adverse event summaries restricted to treatment-emergent AEs (TEAEs) will include those AEs that occurred any time on or after the first in-clinical application of study drug through the last application of study drug and those existing AEs that worsened during this same period. If it cannot be determined whether the AE is treatment emergent due to a partial onset date, then it will be counted as such; see Appendix A for the imputation of missing dates algorithm. Post treatment AEs will include those AEs that occurred after the last application of study drug. Verbatim terms in the eCRFs will be mapped to preferred terms and system organ classes using the MedDRA Version 23.0 or later.

Each AE summary will be displayed by treatment group. Summaries that are displayed by system organ classes and preferred terms will be ordered by descending order of incidence in SB206 treatment group of system organ class and preferred term within each system organ class. Summaries of the following types will be presented:

- Overall summary of TEAEs and post treatment AEs that contain an overview of each item below.

- Subject incidence of TEAEs with total number of unique TEAEs and post treatment AEs with total number of unique post treatment AEs by MedDRA system organ class and preferred term.
- Subject incidence of TEAEs and post treatment AEs by MedDRA system organ class, preferred term, and maximum severity. At each level of subject summarization, a subject is classified according to the maximum severity if the subject reported 1 or more events. Adverse events with missing severity will be considered severe for this summary.
- Subject incidence of TEAEs by MedDRA system organ class, preferred term, and closest relationship to study drug (Related/Not Related). Related AEs are those reported as “Definite,” “Probable,” or “Possible,” and unrelated AEs are those reported as “Unlikely” or “Unrelated.” At each level of subject summarization, a subject is classified according to the closest relationship if the subject reported 1 or more events. Adverse events with a missing relationship will be considered related for this summary.
- Subject incidence of serious TEAEs with total number of unique serious TEAEs and post treatment serious AEs with total number of unique post treatment serious AEs by MedDRA system organ class and preferred term.
- Subject incidence of TEAEs leading to study drug discontinuation by MedDRA system organ class and preferred term.
- Subject incidence of TEAEs leading to study discontinuation and post treatment AEs leading to study discontinuation by MedDRA system organ class and preferred term.
- Subject incidence of TEAEs leading to death as an outcome by MedDRA system organ class and preferred term.
- Subject incidence of Transient TEAEs, identified based on a search of verbatim terms containing ‘TRANSIENT’.

Separate listings of all AEs, all SAEs, all TEAEs leading to study drug discontinuation, all AEs leading to study discontinuation, ongoing treatment related AEs, and all post treatment AEs will be provided.

The proportion of subjects with scarring and the proportion of subjects with keloid or hypertrophic scarring will be summarized descriptively at each visit.

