2.1.4.2 Clinical Safety

It should be noted some subjects have experienced transient asymptomatic erythema at the application site within 5 minutes of dosing, which typically lasted ≤ 15 minutes. This is due to nitric oxide's vasodilatory pharmacologic effect and is an expected event.

Summaries of the safety analyses of the phase 3 studies ([NI-MC301](#) and [302](#)) are ongoing, and the CSRs are under preparation. The treatment emergent adverse event (TEAE) profile of SB206 through the Week 24 was found to be favorable and was very similar between the two studies. Study drug discontinuations in the SB206 treatment arm were all due to application site reactions and no treatment-related serious adverse events were reported across both studies.

Table 2 Overall Summary of TEAEs (Safety Population) through Week 24

	NI-MC301		NI-MC302	
	Vehicle (n=116)	SB206 (n=235)	Vehicle (n=117)	SB206 (n=237)
Subjects who reported at least one TEAE	36 (31.0%)	115 (48.9%)	30 (25.6%)	120 (50.6%)
Serious TEAE	0	0	1 (0.9%)	1 (0.4%)
Treatment-related TEAE	19 (16.4%)	86 (36.6%)	8 (6.8%)	86 (36.3%)
TEAE leading to study drug discontinuation	1 (0.9%)	7 (3.0%)	1 (0.9%)	17 (7.2%)

The TEAEs reported in greater than 5% of subjects in the SB206 treated groups were application site pain and application site erythema, with the majority of these TEAEs being mild or moderate in severity.

Table 3 TEAEs in $\geq 2\%$ of subjects in either SB206 treated group or Vehicle group (NI-MC301)

	Vehicle (n=116)			SB206 (n=235)		
	Mild	Moderate	Severe	Mild	Moderate	Severe
Application site pain	8 (6.9%)	0	0	34 (14.5%)	16 (6.8%)	1 (0.4%)
Application site erythema	2 (1.7%)	1 (0.9%)	0	13 (5.5%)	15 (6.4%)	1 (0.4%)
Application site pruritus	0	0	0	8 (3.4%)	2 (0.9%)	1 (0.4%)
Pyrexia	3 (2.6%)	1 (0.9%)	0	7 (3.0%)	4 (1.7%)	0
Application site exfoliation	0	0	0	4 (1.7%)	5 (2.1%)	1 (0.4%)
Application site scar	9 (7.8%)	0	0	6 (2.6%)	0	0
Application site swelling	1 (0.9%)	0	0	5 (2.1%)	1 (0.4%)	0
Application site dermatitis	1 (0.9%)	0	0	1 (0.4%)	3 (1.3%)	1 (0.4%)
Application site discolouration	0	0	0	5 (2.1%)	0	0
Vomiting	1 (0.9%)	0	0	2 (0.9%)	5 (2.1%)	0
Upper respiratory tract infection	2 (1.7%)	0	0	3 (1.3%)	2 (0.9%)	0

Table 4 TEAEs in $\geq 2\%$ of subjects in either SB206 treated group or Vehicle group (NI-MC302)

[figure not shown]
	Vehicle (n=117)			SB206 (n=237)		
	mild	moderate	severe	mild	moderate	severe
Application site pain	1 (0.9%)	1 (0.9%)	0	15 (6.3%)	22 (9.3%)	0

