14.2.3.2	Summary of a 90% Reduction in Lesion Counts from Baseline at Weeks 2, 4 and 8	ITT
14.2.3.3	Summary of a 75% Reduction in Lesion Counts from Baseline Response by Visit	ITT
14.2.3.4.1	Change from Baseline in Lesion Count by Visit	ITT
14.2.3.5	Complete Clearance Lesion Count Response at Weeks 2 and 4	ITT
14.2.3.6.1	Kaplan-Meier Estimates of Time to Complete Clearance (Days) from Start of Dosing	ITT
14.2.3.7	Summary of Recurrence after Complete Clearance	ITT
14.2.3.8	Summary of Increase in Subject-Reported Spread to Household Members by Visit	ITT
14.2.3.9.1	Summary of Global Severity Assessment by Assessor and Visit	ITT

Table Number	Table Title	Analysis Population
14.2.3.10.1	Summary of Global Impression of Change by Assessor and Visit	ITT
14.2.3.10.4	Summary of Efficacy by Subject Global Impression of Change Improvement at Week 12	ITT
14.2.3.11	Analysis of Correlation of Lesion Count with Global Severity Assessment and Global Impression of Change	ITT
14.2.3.12.1	Analysis of Lesion Counts by Dichotomized BOTE Score	ITT
14.2.3.12.2	Summary of Lesion Counts by Highest Post-Baseline Dichotomized BOTE Score	ITT
14.2.3.12.3	Summary of Lesion Counts by Highest Dichotomized BOTE Score	ITT
14.2.3.12.4	Summary of Percent Change from Baseline in Lesion Count over Time by Dichotomized Week 2 BOTE Score	ITT
14.2.3.12.5	Summary of the Beginning of the End (BOTE) Inflammation Score Results by Visit	ITT
14.3	Safety data	
14.3.1	Displays of Adverse Events	
14.3.1.1.1	Overall Summary of Treatment-Emergent Adverse Events	Safety
14.3.1.1.2	Overall Summary of Post Treatment Adverse Events	Safety
14.3.1.2.1	Summary of Treatment-Emergent Adverse Events by System Organ Class and Preferred Term	Safety
14.3.1.2.2	Summary of Post Treatment Adverse Events by System Organ Class and Preferred Term	Safety
14.3.1.3.1	Summary of Treatment-Emergent Adverse Events by System Organ Class, Preferred Term, and Maximum Severity	Safety
14.3.1.3.2	Summary of Post Treatment Adverse Events by System Organ Class, Preferred Term, and Maximum Severity	Safety
14.3.1.4	Summary of Treatment-Emergent Adverse Events by System Organ Class, Preferred Term, and Relationship to Study Drug	Safety
14.3.1.5.1	Summary of Serious Treatment-Emergent Adverse Events by System Organ Class and Preferred Term	Safety
14.3.1.5.2	Summary of Serious Post Treatment Adverse Events by System Organ Class and Preferred Term	Safety

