14.3.1.6	Summary of Treatment-Emergent Adverse Events Leading to Study Drug Discontinuation by System Organ Class and Preferred Term	Safety

Table Number	Table Title	Analysis Population
14.3.1.7	Summary of Treatment-Emergent Adverse Events Leading to Death by System Organ Class and Preferred Term	Safety
14.3.1.8.1	Summary of Treatment-Emergent Adverse Events Leading to Study Discontinuation by System Organ Class and Preferred Term	Safety
14.3.1.8.2	Summary of Post Treatment Adverse Events Leading to Study Discontinuation by System Organ Class and Preferred Term	Safety
14.3.1.9	Summary of Transient Treatment-Emergent Adverse Events by System Organ Class and Preferred Term	Safety
14.3.2	Listings of deaths, other serious and significant adverse events	
14.3.2.1	Listing of Serious Adverse Events	Safety
14.3.2.2	Listing of Adverse Events Leading to Study Drug Discontinuation	Safety
14.3.2.3	Listing of Deaths	Safety
14.3.6	Other safety data	
14.3.6.1.1	Summary of Local Skin Reaction (LSR) Composite Score by Visit	Safety
14.3.6.1.2	Summary of Local Skin Reaction (LSR) Score Results by Visit	Safety
14.3.6.1.3	Shift Summary of Local Skin Reaction (LSR) Score Results by Visit	Safety
14.3.6.1.4	Summary of Local Skin Reaction (LSR) Composite Score by Dichotomized Baseline BOTE Score and Visit	Safety
14.3.6.1.5	Summary of Local Skin Reaction (LSR) Individual Score by Dichotomized Baseline BOTE Score and Visit	Safety
14.3.6.2	Summary of Events of Special Interest	Safety
14.3.6.3	Summary of Physical Examination Findings	Safety
14.3.6.4	Summary of Scarring and Keloid by Visit	Safety
14.3.6.5	Summary of Patch Testing Results	Safety

Figure Number	Figure Title	Analysis Population
14.2.1.5	Forest Plot: Odds Ratio (95% CI) of the Proportion of Subjects with Complete Clearance at Week 12	ITT
14.2.2.4.2	Percent Change from Baseline in Lesion Count over Time by Treatment Group	ITT
14.2.3.4.2	Mean Change from Baseline in Lesion Count over Time by Treatment Group	ITT
14.2.3.6.2	Kaplan-Meier Plot of Time to Complete Clearance (Days) from Start of Dosing	ITT
14.2.3.9.2	Cumulative Distribution Function Plot Across Subject Global Severity Assessment Responses	ITT
14.2.3.9.3	Cumulative Distribution Function Plot by Subject Global Severity Assessment Severity Category	ITT
14.2.3.10.2	Cumulative Distribution Function Plot Across Subject Global Impression of Change Responses	ITT

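### Relationship and study-drug-discontinuation tables cover only AEs starting by the last application, so a later-onset reaction that ends treatment is in neither

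*SAP*

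**What the plan says.** SAP section 13.1 starts the TEAE period at the first in-clinic application and runs it "through the last application of study drug and those existing AEs that worsened during this same period". It then states: "Post treatment AEs will include those AEs that occurred after the last application of study drug". Protocol section 10.3.4.1 uses the same end point.

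For study drug discontinuation, SAP 13.1 plans "Subject incidence of TEAEs leading to study drug discontinuation by MedDRA system organ class and preferred term", and Appendix C lists the matching Table 14.3.1.6, "Summary of Treatment-Emergent Adverse Events Leading to Study Drug Discontinuation by System Organ Class and Preferred Term". For causality, Appendix C lists Table 14.3.1.4, "Summary of Treatment-Emergent Adverse Events by System Organ Class, Preferred Term, and Relationship to Study Drug". Neither has a post treatment counterpart.

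Leaving the study is handled differently. There the SAP plans "Subject incidence of TEAEs leading to study discontinuation and post treatment AEs leading to study discontinuation by MedDRA system organ class and preferred term", with a table for each period (14.3.1.8.1 and 14.3.1.8.2).

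**The concern.** Study drug is applied once daily. A reaction can start between two doses and be the reason the next dose is never applied. If its onset is dated after the final application, it is a post treatment AE, even though it caused the discontinuation. Table 14.3.1.6 is the natural place to look for such an event, and it is not there. If the investigator calls it related, it is missing from Table 14.3.1.4 too.

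The trial's own procedures make this possible:

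- Protocol 8.6 has the diary remind subjects not to dose at home on visit days. A reaction dated to the visit day that leads to stopping before the in-clinic dose therefore follows the last application.
- Protocol 7.2.4 makes scars AEs to be rated for relatedness, with an assessment at Week 24, about 12 weeks after dosing is planned to end.
- The application-site part of Events of Special Interest (SAP 13.3) is also restricted to TEAEs, so it does not recover these events.

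At stake are two headline tolerability figures for a topical drug whose main known harm is application site reactions. The report could also contradict itself: disposition (SAP 9.1) counts treatment stopped for an AE regardless of onset, so it could exceed the number in Table 14.3.1.6 with no table explaining the gap.

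**Working it through.** **Step 1. Which summaries cover which period (SAP 13.1 against Appendix C).**

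| Summary | TEAE table | Post treatment table |
|---|---|---|
| Overview | 14.3.1.1.1 | 14.3.1.1.2 |
| System organ class and preferred term | 14.3.1.2.1 | 14.3.1.2.2 |
| Maximum severity | 14.3.1.3.1 | 14.3.1.3.2 |
| Relationship | 14.3.1.4 | none |
| Serious | 14.3.1.5.1 | 14.3.1.5.2 |
| Leading to study drug discontinuation | 14.3.1.6 | none |
| Leading to study discontinuation | 14.3.1.8.1 | 14.3.1.8.2 |

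The death (14.3.1.7) and transient-event (14.3.1.9) tables are also TEAE-only. A late death would still appear in the post treatment serious table and the death listing, so those are not part of this point.

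**Step 2. Follow one event.** Let D be the day of the final application.

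- Onset on day D: TEAE, in both tables.
- Onset during a hold, with treatment later restarted: TEAE, because the last application comes afterwards.
- Partial onset date that cannot be placed: counted as a TEAE.
- Known onset on D+1 or later, no further dose: post treatment, in neither table.

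Only the last case is lost from the two tables.

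**Step 3. Which arm would lose more.** Inputs are the TEAEs leading to drug discontinuation in Protocol Table 2. The printed percentages recompute: SB206 7/235 = 3.0% and 17/237 = 7.2%; vehicle 1/116 = 0.9% and 1/117 = 0.9%.

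- SB206 pooled: (7 + 17)/(235 + 237) = 24/472 = 5.1%
- Vehicle pooled: (1 + 1)/(116 + 117) = 2/233 = 0.9%
- Difference: 4.2 percentage points
- At 425 per arm: 425 × 24/472 = 21.6 and 425 × 2/233 = 3.6 subjects

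**Step 4. Illustration only.** The documents do not give the share f of these reactions that start after the last dose. Assume the same f in both arms and multiply each count by (1 − f):

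| Assumed f | SB206 | Vehicle | Difference (points) |
|---|---|---|---|
| 0 | 21.6 | 3.6 | 4.2 |
| 5% | 20.5 | 3.5 | 4.0 |
| 10% | 19.4 | 3.3 | 3.8 |
| 20% | 17.3 | 2.9 | 3.4 |
| 30% | 15.1 | 2.6 | 3.0 |

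With equal f, SB206 bears 21.6/(21.6 + 3.6), or about 86%, of the missing events at 1:1 allocation.

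**The case against.** The strongest reply is that this is a prespecified convention, identical in protocol and SAP, that safety is descriptive, and that late events are reported separately rather than discarded. Much of that stands.

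- **A reader might infer that the events vanish from the report.** They do not. They are in the post treatment tables listed above, in Listings 16.2.7.1 and 16.2.7.4, and in disposition, where AE is one of the recorded reasons for stopping treatment (Protocol 6.8.2.2). Scars have a by-visit table (14.3.6.4) with no TEAE restriction. Suspected allergic contact dermatitis, hypertrophic or keloid scarring and unresolved scars go into the narrative listing (SAP section 6).
- **A reader might take the length of follow-up after dosing as the size of the loss.** Time off drug is not a count of related events. The share of time is not fixed either: Week 12 is Day 85 ± 5, so a last dose on Day 90 leaves 169 − 90 = 79 of 169 days (47%).
- **A reader might conclude that the results cannot be compared with Protocol Table 2.** Its title, "Overall Summary of TEAEs (Safety Population) through Week 24", gives a reporting period. The TEAE definition behind it is not in the documents, so non-comparability is not shown.
- **The mechanism is narrow.** Protocol 6.8.2 recommends a short hold and restart after a first reaction. Allergic contact dermatitis is suspected only after re-exposure, so many reactions precede a later dose.

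The post treatment overview might also carry related and drug-discontinuation counts, since SAP 13.1 says the overview spans every item listed. The text does not settle which rows it has, and such counts would not be by preferred term.

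None of this supplies the two missing tables. Disposition gives a number without the event terms, and the scar table is not split by relationship.

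**Conclusion.** The gap is real and specific. Two summaries, relationship and study drug discontinuation, stop at the last application, while the comparable summaries continue afterwards. A reaction with known later onset that ends treatment is absent from both, or from the relationship table alone where it plays no part in stopping; a related scar with first onset at Week 24 is an example of the latter.

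The size of the undercount cannot be derived from the documents. The 5% to 30% range above is an assumption, as is equal f across arms. That a loss would fall mainly on SB206 is probable rather than established: it rests on the earlier 24/472 against 2/233, which are themselves TEAE counts.

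This is not a conflict between protocol and SAP, and it does not affect efficacy. It is a cheap improvement worth making before unblinding.

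**What to change.** 1. Keep the TEAE definition and the existing TEAE tables.
2. Tabulate AEs leading to study drug discontinuation by preferred term whatever the onset date relative to the last dose, flagging onsets after the last application. Check the total against the disposition count.
3. Add a post treatment version of Table 14.3.1.4, or one running through Week 24/ET2.
4. Reconcile the listing of drug discontinuations: SAP 13.1 restricts it to TEAEs, while the title of Listing 14.3.2.2 in Appendix C carries no such restriction.
5. Record the additions in SAP section 14, which now reports no changes from the protocol. Do so before the Week 12 freeze and unblinding described in SAP section 6.

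The cost is two extra descriptive tables from data already collected. The downside is that some late AEs unrelated to the drug will enter the relationship summary.
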